## **Mechanism for Monitoring Patient Safety**

### Known Potential Toxicity of Study Drug

In trials of sildenafil in patients without contraindications to drug administration, adverse effects were generally mild to moderate and transient in nature. The overall frequency of discontinuation in Revatio® -treated patients at the recommended dose of 20 mg t.i.d. was low (3%) and the same as placebo (3%) Side effects that occurred in more than 2%, and more frequently by patients on study drug than on placebo included headache (67% vs. 56%) epistaxis (13% vs. 2%) flushing (15% vs. 6%) , dyspepsia (19% vs. 10%), nasal congestion (6% vs. 0%), insomnia (11% vs. 2%), erythema (9% vs. 2%), exacerbation of dyspnea (11% vs. 5%), diarrhea (13% vs. 9%) , myalgia (11% vs 6%), pyrexia (9% vs 5%), gastritis (5% vs 0%), sinusitis (5% vs 0%) and paresthesia (5% vs 0%.) At doses *higher than the recommended dose* of 20mg t.i.d., incidence of adverse events of some symptoms was increased including flushing, diarrhea, myalgia and visual disturbances (mild and transient color-tinge, sensitivity to light or blurred vision.) Incidence of retinal hemorrhage in subjects taking the recommended dose was 1.9% vs placebo and occurred in patients on anti-coagulation. Patients in this study will not be on anticoagulation. There was no report of priapism in the placebo controlled trial of

Revatio®. Post-marketing experience of Viagra® (dosed as 50-100 mg once daily for erectile dysfunction), has demonstrated serious cardiovascular, cerebrovascular and vascular events, as well as priapism and ischemic retinopathy. Very rarely, cases of decreased hearing have been reported in patients taking Viagra. It is not clear if this was related to taking Viagra or the patients' medical conditions. These adverse events were not seen in the randomized, placebo-controlled trial of Revatio® for pulmonary hypertension. The majority of these events occurred in patients with preexisting cardiovascular risk factors. Patients with cardiovascular risk factors will not be included in the study. Revatio® did cause transient decreases in supine blood pressure in healthy volunteers (mean maximum decrease in systolic/diastolic blood pressure 8.4/5.5mmHg.) Subjects in this study will have monitoring of their blood pressure following administration of the initial doses of study drug. Cases of sudden decrease or loss of hearing have been reported post-marketing in temporal association with the use of phosphodiesterase inhibitors. In some cases, medical and other factors were reported that may also have played a role in the otologic adverse events. It was not possible to determine whether these reported events are directly related to the use of phosphodiesterase inhibitors, to the patient's underlying risk factors for hearing loss, or a combination of these factors. No hearing loss related to sildenafil administration was observed in CF subjects who participated in the pilot study performed at our institution.

### Adverse Events (AE)

An adverse event will be defined as any unfavorable and unintended sign, symptom, or disease temporally associated with the use of Revatio® or other protocol-imposed intervention, regardless of attribution.

This definition will include the following:

- AEs not previously observed in the subject that emerge during the study period, including signs or symptoms associated with CF that were not present prior to the study period
- Complications that occur as a result of protocol-mandate interventions
- Preexisting medical conditions (other than the condition being studied) judged by the investigator to have worsened in severity or frequency or changed in character during the protocol-specified AE reporting period

Subjects will be questioned and/or examined by the Investigator or her designee for evidence of adverse events.

Subjects having adverse events will be monitored with relevant clinical assessments and laboratory tests as determined by the investigator. All adverse events will be followed to satisfactory resolution or stabilization of the event(s.) Any actions taken and follow-up results will be recorded on the appropriate page of the CRF, as well as in the subject's source documentation. Follow-up laboratory results will be filed with the subject's source documentation.

For all adverse events that require the subject to be discontinued from the study, relevant clinical assessments and laboratory tests will be repeated until satisfactory resolution or stabilization of the event(s.)

A serious event will be determined as follows:

- It results in death
- It is life threatening
- It requires or prolongs inpatient hospitalization
- It results in persistent or significant disability/incapacity
- It results in a congenital anomaly/birth defect in a neonate/infant born to a mother exposed to the investigational product
- It is considered a significant medical event by the investigator based on medical judgment

Grading of AEs will be as follows:

- Mild: Transient or mild discomfort (<48 hours); no interference with the subject's daily activities; no medical intervention/therapy required
- Moderate: Mild to moderate interference with the subject's daily activities; no or minimal medical intervention/therapy required

- Severe: Considerable interference with the subject's daily activities; medical intervention/therapy required; hospitalization possible

To determine the causality of AE and SAE the follow guidelines will be assessed:

- Probably related

There is a plausible temporal relationship between the onset of the AE and administration of Revatio®, and the AE cannot be readily explained by the subject's clinical state, intercurrent illness, or concomitant therapies; and/or the AE abates or resolves upon discontinuation Revatio®.

- Possibly related

There is a plausible temporal relationship between the onset of the AE and administration of Revatio®, and an alternative etiology (e.g., preexisting medical condition, underlying disease, intercurrent illness, or concomitant medication) for the AE is equally or more likely than the potential relationship to administration of Revatio®.

- Not related

Evidence exists that the AE has an etiology other than administration of Revatio® (e.g., preexisting medical condition, underlying disease, intercurrent illness, or concomitant medication); and/or the AE has no plausible temporal relationship to administration of Revatio® (e.g., cancer diagnosed 2 days after first dose of study drug.)

In this pilot study, it is unlikely that there would be early (i.e. before study completion) demonstration of efficacy or futility. However, unanticipated serious adverse events would result in early termination of the study.

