In concert, these studies suggest that PDEis might be a way to reconcile both the sodium and chloride ion transport defects present in the CF lung, and may also address other downstream effects resulting from TGN hyperacidification found in CF, including disordered CFTR glycosylation, a predisposition to *P. aeruginosa*, and excessive inflammation. Based on the *in vitro* data suggesting a possible role for PDEi as anti-inflammatories in CF, we designed a single site open-label dose escalation study (Clinicaltrials.gov No.: NCT00659529) to evaluate the safety, efficacy and pharmacokinetics of sildenafil in subjects with mild to moderate CF lung disease. On study day 1, subjects underwent exhaled breath condensate (EBC) measurement, lung function and routine laboratory testing, completed the CF Health Related Quality of life questionnaire (CFQ-R), and had sputum collected for bacterial counts and sputum biomarkers. Subjects received oral sildenafil 20 or 40 mg p.o. t.i.d. for 6 weeks, and all evaluations were repeated at the end of 6 weeks. Twenty subjects completed the

study. There were no drug-related serious adverse events, and side effects were generally mild and consistent with those previously reported. There was improvement in the primary endpoint, mean sputum elastase ( $p < 0.03$ ), which is a sensitive measure of CF airway inflammation and has been shown to predict lung function decline in patients with CF. There was also a non-significant trend towards improvement in sputum IL-8 ( $p = 0.13$ ). There was no difference in EBC pH, the respiratory score of the CFQ-R, or sputum microbiology ( $p = 0.44$ ,  $p = 0.88$  and  $p = 1.0$ , respectively).

Given the relative ease of testing this approach due to the clinical availability of sildenafil and other PDEis, these results suggest a strong need to also study the ion transport effects of sildenafil in CF. This study represents an excellent opportunity to capitalize on the safety and tolerability assessments already completed at our institution.

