### Sildenafil as candidate drug

Protein kinase G-dependent smooth muscle relaxation occurs in response to elevated levels of cGMP. Inhibition of phosphodiesterase type 5 (PDE-5,) which is responsible for degradation of cGMP, or stimulation with nitric oxide (NO) can cause this effect. Sildenafil (Revatio, Pfizer) is a PDE-5 inhibitor. Sildenafil-induced increased cGMP concentration leads to pulmonary vasculature smooth muscle relaxation. It is this effect that is key in treatment of pulmonary hypertension by sildenafil.

A case study reported on the use of sildenafil in a patient with severe CF lung disease (genotype  $\Delta F508/G551D$ , FEV1 1.051, 23% predicted) complicated by exercise-induced pulmonary hypertension. Treatment with 1 week of oral sildenafil 25 mg twice a day, followed by 4 months of 25 mg four times a day, lead to physiological improvement, and decreased subjective complaints of dyspnea and chest pain with exertion within 2 weeks of starting therapy. Improvements in exercise tolerance were increased further after 4 months of therapy. Sildenafil was well-tolerated with no adverse events. Although these effects were attributed to the reduction in pulmonary artery pressure, the more prolonged and sustained improvement suggests the possibility for a more global effect on the ion transport abnormality, and also demonstrates the relative safety of this agent even in individuals with severe lung disease.

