**Aim 3. Further evaluate the safety and tolerability of sildenafil in subjects with CF**

- a. Evaluate the effect of sildenafil on treatment emergent adverse events
- b. Evaluate the effect of sildenafil on change in clinical laboratory measures, vital signs and physical exam findings

Primary Endpoints

Na+ conductance by nasal potential difference (within subject change in maximum basal PD)

Secondary Endpoints

Other measures of Na transport (mean basal PD, end-ringers profusion PD, change in PD with amiloride)  
 Cl conductance by NPD (total Cl conductance, change in PD with chloride free solution, change in PD with isoproteronol, total change in NPD (delta NPD))  
 Sweat Na+ by pilocarpine iontophoresis  
 Sweat Cl concentration by pilocarpine iontophoresis  
 Pulmonary function by spirometry  
 Lung clearance index  
 Exhaled nitric oxide (eNO)  
 Sputum nitric oxide metabolites  
 Safety and tolerability (including laboratory studies, CFQ-R)

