**Exclusion criteria:**

- 1) History of hypersensitivity to sildenafil
- 2) Use of an investigational agent within the 4-week period prior to Visit 1 (Day 0)
- 3) Breastfeeding, pregnant, or verbal expression of unwillingness to practice an acceptable birth control method (abstinence, hormonal or barrier methods, partner sterilization or intrauterine device) during participation in the study
- 4) History of significant hepatic (SGOT or SGPT > 3 times the upper limit of normal at screening, documented biliary cirrhosis, or portal hypertension), cardiovascular (history of aortic stenosis, coronary artery disease, pulmonary hypertension with right ventricular systolic pressure >55 mmHg or life-threatening arrhythmia), neurological (history of stroke), hematologic (history of bleeding diathesis), ophthalmologic (history of retinal impairment or non-arteritic ischemic optic neuritis) or renal impairment (creatinine >1.8 mg/dL.)
- 5) Inability to swallow pills
- 6) Previous lung transplantation
- 7) Use of concomitant nitrates,  $\alpha$ -blocker, or Ca channel blocker
- 8) Use of concomitant medications known to be potent inhibitors of CYP3A4 (e.g. ketoconazole, itraconazole, ritonavir, clarithromycin, erythromycin, rifampin, verapamil)
- 9) Presence of a condition or abnormality that in the opinion of the investigator would compromise the safety of the subject or the quality of the data
- 10) Weight less than 40 kg
- 11) History of sputum or throat swab culture yielding *Burkholderia cepacia* within 2 years of screening
- 12) History of nasal disease or nasal surgery that would, in the opinion of the investigator, impede accurate measurements of NPD
- 13) Use of anticoagulant medication (e.g. heparin, coumadin)
- 14) Resting room air oxygen saturation <93%
- 15) Use of nighttime oxygen
- 15) History of migraine headaches
- 16) Baseline BP of < 90/50 mm Hg

Study Design

This study is a randomized, placebo-controlled, double blind study of sildenafil (Revatio) in clinically stable patients with mild-moderate CF lung disease. The length of participation for each subject will be approximately 6 weeks, and will consist of a screening visit, 4 out-patient visits, and a follow-up phone assessment 2 weeks after subject's study completion.

Randomization

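### Does a relatedness scale worded around Revatio® force adverse event raters to know the treatment arm?

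*Combined protocol and SAP*

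**What the plan says.** The causality guidance in the Adverse Events (AE) section has three categories: probably, possibly and not related. Each is framed around Revatio®. The first opens: "There is a plausible temporal relationship between the onset of the AE and administration of Revatio®, and the AE cannot be readily explained". The last ends with a clause that uses two terms for the product in one breath: "the AE has no plausible temporal relationship to administration of Revatio® (e.g., cancer diagnosed 2 days after first dose of study drug".

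Elsewhere the brand name means the active drug. The section Sildenafil as candidate drug states "Sildenafil (Revatio, Pfizer) is a PDE-5 inhibitor", and Study Design states "This study is a randomized, placebo-controlled, double blind study of sildenafil (Revatio", followed by the closing bracket. The definition of an adverse event, in the same section as the scale, is wider. It covers anything "temporally associated with the use of Revatio® or other protocol-imposed intervention, regardless of attribution".

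On blinding, Study Design declares the trial double blind. Dosing gives placebo subjects a sham escalation, and Study Drug describes blinded bottles dispatched by sequence number. Randomization says the pharmacist passes the randomization to the site coordinator, without saying in what form. Outcome measurements and Procedures schedules sildenafil troughs at visits 2, 3 and 4, without saying who receives the results. The only role described individually as blinded is the reader of the nasal potential difference (NPD) tracings.

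**The concern.** A causality scale in a blinded trial should refer to the blinded product. Here it names the active one. Taken at its word, a placebo subject was never given Revatio®, so neither of the two related categories can be met and every placebo event falls into not related. A rater applying the words strictly would have to know the arm first.

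If that happened and relatedness were then tabulated by arm, the comparison would lose its placebo background and sildenafil would look worse tolerated than it is. Aim 3 includes "Evaluate the effect of sildenafil on treatment emergent adverse events", and the team summarised its earlier pilot partly by relatedness: "There were no drug-related serious adverse events, and side effects were generally mild". A table of related events is therefore conceivable.

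Two silences add to the worry. If the pharmacist's message to the coordinator carried the arm, or if the visit 3 and visit 4 troughs came back to the site, someone who collects or rates adverse events could learn the allocation. The research coordinator makes the visit 5 adverse event call.

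**Working it through.** **1. Does the scale require knowledge of the arm?** Set the places side by side.

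| Place | What it establishes |
|---|---|
| Adverse Events (AE), causality | Categories name Revatio®; the example under not related says study drug |
| Adverse Events (AE), definition | Reaches any protocol-imposed intervention, whatever the attribution |
| Study Design | Double blind |
| Dosing | Sham escalation on placebo |
| Study Drug | Blinded bottles, shipped by sequence number |
| Randomization | Pharmacist informs the coordinator; form unstated |
| Outcome measurements and Procedures | Troughs drawn; recipient unstated |

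Nothing tells a rater to find out the allocation. The scale changes term within one sentence, so it treats the two as the same thing. A blinded rater judges the event against the timing of the bottle the subject received, and the scale then works identically in both arms. The literal reading would contradict the double-blind design; the shorthand reading is consistent with every row.

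**2. Do the two silences unblind anyone?** Supply by sequence number makes a blinded number the natural content of the pharmacist's message. The troughs could separate the arms if seen, but no passage sends them to a rater. Both are omissions of operational detail, not contradictions.

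**3. Does anything depend on relatedness?** Data Analysis names no adverse event test. The termination sentence in the Adverse Events (AE) section and the Criteria for Participant Discontinuation do not use the category. Aim 3 concerns treatment-emergent events. NPD scoring is done off site by a blinded reader, sweat is assayed in a core laboratory, and counts of all adverse events do not involve the scale.

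**4. How large could the effect be if the literal reading were applied?** The plan has no figure of its own to reproduce. Inputs: 12 sildenafil and 6 placebo subjects (Sample size), and headache rates from Known Potential Toxicity of Study Drug, "on study drug than on placebo included headache (67% vs. 56" percent. Let s be the share of placebo events moved to not related. The placebo related rate is 0.56 × (1 − s).

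- Expected headaches: 12 × 0.67 = 8.04 and 6 × 0.56 = 3.36.
- s = 0: 67% − 56% = 11 points. s = 1: 67% − 0% = 67 points.
- Fisher's exact test, used only to show scale: 8/12 against 3/6 gives p = 0.63; 8/12 against 0/6 gives p = 0.013.

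The chance of p ≤ 0.05 with the higher rate on sildenafil is summed exactly over the two binomials:

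| Assumed related rates before reclassification | s = 0 | s = 0.75 | s = 1 |
|---|---|---|---|
| Headache, all rated related (67% / 56%) | 4.1% | 50.4% | 82.9% |
| Headache, half rated related (33.5% / 28%) | 1.1% | 4.5% | 6.8% |
| Dyspepsia, all rated related (19% / 10%) | 0.2% | 0.2% | 0.3% |
| Flushing, all rated related (15% / 6%) | 0.1% or less | 0.1% or less | 0.1% or less |

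The value s = 0.75 takes the arm as known from visit 3 onward, 21 of 28 treatment days, with events spread evenly. The large figures appear only for the commonest event with every occurrence called related.

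**The case for a change.** The best case for acting is that a rating rule should not depend on guessing what its author meant. The two readings classify placebo events differently, ratings cannot be fully repaired once recorded, and the remedy is a few words. The plan takes care to name a blinded NPD reader but gives no matching statement for the investigator or designee who assesses adverse events. The troughs have a stated purpose, checking the Orkambi interaction, so somebody must look at them. The pilot's report by relatedness suggests this trial may do the same.

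Much of that is true as description. The terms are mixed, and neither the pharmacist's message nor access to the troughs is spelled out. What fails is the step to a distorted result. It needs a rater who knows the arm and who then also reads the brand name literally; the plan supports neither. The pilot was open-label with no placebo arm, so its summary by relatedness says little about how arms would be compared here. The documents do not say that relatedness will be tabulated by arm, and if it is, a rater who stayed blinded produces a fair comparison under the existing words.

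**Conclusion.** The concern does not hold as a defect in the plan. Using the brand name for the blinded product is a clerical slip whose intended meaning is clear from the double-blind design, the sham escalation, the blinded bottles and the scale's own use of study drug. The handling of the pharmacist's message and of the trough results is operational detail that a blinded trial team would ordinarily settle in its working procedures.

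Under the natural reading the effect on any stated analysis is nil: no endpoint, test, termination rule or discontinuation criterion uses relatedness. The shift from 11 to 67 points is the extreme of a chain of assumptions without support in the documents, and it largely disappears for less common events or when only half of headaches are rated related. The conclusion rests on raters staying blinded, as the design declares. Evidence that trough results or allocations reached the people rating adverse events would be a separate matter of trial conduct, and rewording the scale would not cure it.

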#### Criteria for Participant Discontinuation

- Severe dyspnea at rest
- Pregnancy
- Subject refusal to continue in study
- Development of an adverse event that the investigator feels is a preclusion to continued subject participation

#### Data Safety Monitoring Board (DSMB.)

Oversight for this trial will be conducted by the Cystic Fibrosis Foundation Therapeutics Development Network DSMB

#### Pregnancy

If a subject or subject's partner becomes pregnant during the study, the subject will be discontinued from the study. We will not request to follow the pregnancy or the offspring.

[figure not shown]

## STUDY TIMELINE

## STUDY FLOWCHART

	Screening/ Pretherapy	Baseline	Treatment	Treatment	Follow-up call
Visit	1	2	3	4	5
Day(s)	0	1	8±3	29+3	43±3
Informed consent	x				
Demographics	x				
Medical history	x				
Concomitant medications and airway clearance	x	x	x	x	x
Bacterial colonization	x				
Vitals signs	x	x	x	x	
Spirometry	x	x		x	
Height	x				
Weight	x	x		x	
CFQ-R		x		x	
Complete physical examination	x	x		x	
Safety labs	x	x		x	
Sildenafil Trough		x	x	x	
Pregnancy Test	x			x	
Nasal Potential Difference		x	x	x	
Sweat testing		x	x	x	
Lung clearance index		x	x	x	
EKG	x				
Study drug dispensed		x	x		
Study drug bottle return			x	x	
Adverse events		x	x	x	x
